In addition to this primary analysis of the intermediate factors that is restricted to those not compliant/adherent at discharge, a supplemental analysis will assess the proportion compliant at 3, 6, and 12 months regardless of compliance at month 0 (i.e., proportion compliant/adherent in the entire population). This analysis will consider a mixed modeling approach with outcomes at 4 time points (0, 3, 6, and 12 months). The focus of this analysis will be on the change in the proportion compliant between month 0 and 12 months (but also reporting the change in the proportion to 3 and 6 months). In addition to assessing treatment differences in the change in the proportion, the treatment differences in the proportions at the 4 time points will be assessed.

For all six factors, analyses assessing the potential for bias from missingness will be performed using inverse probability weighting (for both the analysis restricted to those not compliant/adherent and for the entire population analysis). This will be conducted by first developing a logistic regression model estimated in all subjects predicting the probability of observing the 12-month observation. Predictors in the model will be site (with cluster randomization, implicitly including treatment effect), age, NHW race/ethnicity, sex, NIHSS and nSES. The inverse of this probability will be standardized by dividing by the sum of the inverses, standardizing the inverse probabilities to have the same sum as the sample size; hence, not inflating or deflating statistical power. The analysis for the factor will then be repeated using the inverse probability weights. Should the interpretation of results differ between the weighted and unweighted analyses, the primary interpretation will be based on the weighted analysis, and the weighted analysis will be the basis for figures and estimates in the manuscript will focus on the weighted results.

Effect modification will be assessed by age, sex, race/ethnicity, stroke sub-type, stroke severity (discharge NIHSS dichotomized at 0 to 1 versus 2+), and nSES.

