### **3.2. Modified Rankin Score (mRS)**

The mRS is a 7-point scale, ranging from 0 (normal) to 6 (dead), where at baseline the scores were from 0 to 5 (discharged dead were excluded from the study). During follow-up, patients were scored a 6 at the 3, 6 and 12-month follow-up if the patient died before the respective follow-up (even if the patient missed intervening visits). The mRS will be dichotomized as “good outcomes” of 0 to 2 points, and “poor outcomes” of 3 to 6 points. Analysis will use a mixed model approach (implemented through GLIMMIX) with the treatment-specific proportion of “good outcomes” modeled at months 0, 3, 6, and 12 (reported with the p-value for treatment differences at each time point). The primary outcome will be treatment differences in the change in the proportion with good outcomes between months 0 and 12, but differences to months 3 and 6 will also be estimated. These differences will be estimated with the same 4-level incremental adjustments, and with both unadjusted and inverse-probability weighted adjustment. Effect modification will be assessed by age, sex, race/ethnicity, stroke sub-type, stroke severity (discharge NIHSS dichotomized at 0 to 1 versus 2+), and nSES. With the discharge mRS as an outcome, the analysis will not be adjusted for baseline mRS.

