### **3.3. Stroke Impact Scale (SIS)**

The SIS is a continuous outcome variable with a range from 0 to 100 which will be analyzed identically to continuous intervening factors measured at 4 timepoints (including the analysis with inverse probability weighting). We do note that: 1) after approximately half the patients were recruited, a decision was made to not collect SIS at baseline; however, it is quite reasonable to assume that this decision will give rise to data missing at random and the missingness will be addressed by the mixed models, and 2) the baseline SIS collected were the “long form” of the questionnaire (96 items); however, the 16 items in the short form used at 3, 6 and 12 months are a subset of the long form, and these items will be extracted and scored identically with the follow-up assessments. The analysis of SIS will employ analysis for a continuous factor, but will follow the modeling approach described above for mRS, specifically reporting treatment differences in mean SIS rather than treatment differences in the proportion with good mRS outcome (primary outcome as treatment difference in the change in mean SIS between baseline and 12 months, 4-level incremental models, with/without inverse probability weighting, assessment of effect modifiers, etc.).

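### One 12-month weight used for the whole repeated-measures model can create a false treatment difference at month 0 and in the crude month 0 to 12 change, if retention depends on prognosis and also differs by arm

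*SAP*

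**What the plan says.** SAP 3.1 specifies one inverse-probability model for one event, having the month-12 observation: "a logistic regression model estimated in all subjects predicting the probability of observing the 12-month observation". Its predictors are given as "Predictors in the model will be site (with cluster randomization, implicitly including treatment effect), age, NHW race/ethnicity, sex, NIHSS and nSES". The weights are rescaled, "standardizing the inverse probabilities to have the same sum as the sample size", and then: "The analysis for the factor will then be repeated using the inverse probability weights". No separate weight is given for months 3 and 6, there is no statement that month 0 is unweighted, and the records that carry the weight are not named. If the weighted and unweighted interpretations differ, "the primary interpretation will be based on the weighted analysis".

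SAP 3.2 takes this over for the mRS, which is modelled at months 0, 3, 6 and 12 and estimated "with both unadjusted and inverse-probability weighted adjustment". The target there is a change: "The primary outcome will be treatment differences in the change in the proportion with good outcomes between months 0 and 12". SAP 3.3 does the same for SIS: "primary outcome as treatment difference in the change in mean SIS between baseline and 12 months".

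In SAP 3.1 the primary analysis of the six intermediate factors models months 3, 6 and 12 and focuses on month 12. The supplemental whole-population analysis of those factors models all four visits and focuses on the month 0 to 12 change. Both are to be weighted.

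**The concern.** The inverse of the probability of being seen at month 12 restores the full population among patients who are seen at month 12. The discharge mRS is not subject to attrition and needs no such weight. Applied to month-0 records, including those of patients who later drop out, the weight over-represents patients who resemble dropouts. The same holds, to a lesser degree, at months 3 and 6. For mRS and SIS the primary quantity subtracts month 0 from month 12, so a distorted month-0 mean enters it directly. SAP 3.2 also asks for a p-value for the treatment difference at each time point, month 0 included.

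Unequal retention is plausible. In the protocol's arm-specific sections, ISPU patients have monthly visits and a further payment for each intermediate one, while CSC/PSC patients have research visits at 3, 6 and 12 months. Telephone collection of SIS and smRS in both arms lessens this but does not exclude it.

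At stake is the analysis that decides when results disagree. Disagreement is most likely when the weights vary strongly, which is also when the distortion is largest.

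**Working it through.** **Plan's own figure.** The documents give none for the weighted analysis. The only yardstick is the SIS design difference of 2.7 (protocol 9.A: SD 8, intraclass correlation 0.05, 900 per arm, 100 per site). It reproduces: SE = 8 × √(2 × (1 + 99 × 0.05)/900) = 0.920; with t on 16 df, (2.120 + 0.865) × 0.920 = 2.75.

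**Inputs.** The documents give no retention by arm or severity. All retention rates, strata and stratum outcomes below are assumptions. There is no true treatment effect in any case.

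**Formulas.** For stratum share π, retention p and weight w = 1/p:
- month-0 mean = Σπ·w·y₀ / Σπ·w (everyone has a record);
- month-12 mean = Σπ·p·w·y₁₂ / Σπ·p·w = Σπ·y₁₂ (only retained patients have a record), which is correct.

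Rescaling multiplies every weight by a constant and changes neither mean.

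**mRS 0-2, raw weighted means.** 60% mild and 40% severe; good outcome 80%/30% at month 0 and 90%/50% at month 12. Truth: 60.0%, 74.0%, change 14.0 points.

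| Case | Retention mild/severe, CSC/PSC; ISPU | Weighted month 0, CSC/PSC; ISPU | False difference in change, weighted | Unweighted |
|---|---|---|---|---|
| A | 70/70; 90/90 | 60.0; 60.0 | 0 | 0 |
| B | 80/50; 80/50 | 54.2; 54.2 | 0 | 0 |
| C | 80/50; 94.1/80 | 54.2; 58.0 | -3.8 | -2.7 |
| D | 90/80; 94.7/88.9 | 58.6; 59.2 | -0.7 | -0.5 |

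Case C in full:
- CSC/PSC month 0: (0.6/0.8 × 0.80 + 0.4/0.5 × 0.30)/(0.6/0.8 + 0.4/0.5) = 0.84/1.55 = 54.2%.
- ISPU month 0: (0.6375 × 0.80 + 0.50 × 0.30)/1.1375 = 0.66/1.1375 = 58.0%.
- Month 12 is 74.0% in both arms, so the changes are 19.8 and 16.0 and the difference is -3.8.
- Unweighted month 12 is 0.532/0.68 = 78.2% and 0.668/0.885 = 75.5%; month 0 is 60.0% in both arms, so the difference is -2.7.

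In C and D the odds ratio for severity is the same in both arms (for C, odds 4 and 1 against 16 and 4), so no arm-by-severity interaction is needed. In A the weight is constant within arm and cancels. In B each arm's change is wrong (19.8 instead of 14.0), but the difference between arms is not. With weight 1 at month 0 and 1/p at month 12, every case returns to 0.

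**SIS, closed form at month 0.** Two equal strata 12 points apart; retention 92/82 in ISPU and 85/60 in CSC/PSC. The weighted share of severe patients is 0.92/(0.92 + 0.82) = 0.529 and 0.85/(0.85 + 0.60) = 0.586. The false difference is (0.586 - 0.529) × 12 ≈ 0.69 points. At these retention rates, 0.5 to 1.1 points corresponds to strata about 9 to 19 points apart (0.0575 × 9 = 0.52; 0.0575 × 19 = 1.09).

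**SIS, crude mixed model** (random patient intercept, visits 0, 3, 6 and 12).
- *Gap constant at 12 points, same retention.* Patient-level likelihood weights shift the month-12 difference by +0.58, so the change is 0.58 - 0.69 = -0.11. The unweighted change is also -0.11. With record-level weights the month-12 shift is about -0.02.
- *Gap narrowing from 20 to 15 points, case C retention, truth 67 and 74.* Patient-level weights give 64.7 and 66.2 at month 0 (CSC/PSC, ISPU), 72.2 and 73.4 at month 12, and a change difference of about -0.3. Record-level weights give 66.5 and 66.8 at month 0, 74.0 in both arms at month 12, and about -0.3 in change. The unweighted model is within about 0.1 of zero.
- *Other assumed combinations, patient-level weights.* About -0.04 to -0.24 in change and 0.5 to 1.1 at month 0.
- *Severity in the model, gap constant.* 0.00 under every weighting.

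**The case against.** Much can be said for the plan.

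- **A reader might infer that any difference in retention between arms biases the result.** It does not (case A). Retention must also vary within arm with something related to the outcome.
- **A reader might infer that the month-12 estimate is wrong.** That is the visit the weight is built for. It shifts materially only if the weight multiplies each patient's whole likelihood, and the SAP does not specify this.
- **Three of the four incremental models give protection.** NIHSS enters from the second model, and age, sex, race/ethnicity and nSES from the third; site is a random effect throughout. With severity adjusted for and a constant gap, the bias is nil. A main effect does not absorb a severity gap that changes over time, so some residual can remain.
- **The weight does not always add bias.** With a constant gap, the crude change is off by the same -0.11 with or without it.
- **The SAP does not say that every visit's records are weighted.** If only patients with a month-12 record were weighted, at all their visits, the exact calculation gives no false difference. But a model fitted in all subjects, weights summing to the sample size, and a repeat of the same analysis point to all records.
- **Loss may be small.** Protocol section 9 expects little missing data, and deaths are scored on the mRS. With assumed retention of 95/90 against 92/85 and strata 12 points apart, the crude SIS errors are 0.045 at month 12 and -0.01 in change.

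These points limit the size and reach of the problem. They do not make a month-12 weight appropriate for month-0 records.

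**Conclusion.** The point holds in a limited form. Applied as naturally read, the weight distorts the month-0 means. It can put a false treatment difference into month 0 and into the crude month 0 to 12 change for mRS and SIS, provided that retention depends on outcome-related covariates and also differs by arm. The supplemental whole-population analysis of the intermediate factors is exposed in the same way. The primary analysis of those factors has no month-0 contrast; only its month-3 and month-6 results carry a mismatched weight.

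Under assumed retention, the mRS error in change is about -0.7 to -3.8 points as raw weighted means, against -0.5 to -2.7 unweighted. The SIS error, with patient-level weights in the crude mixed model, is about -0.04 to -0.24 points in change and 0.5 to 1.1 at month 0; the heaviest case gave about -0.3 and 1.5. Against 2.7 the SIS change error is small and the month-0 error is not negligible.

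The documents do not support the stronger conclusions that the weighted analysis is biased whenever retention differs by arm, that the adjusted models fail generally, or that the month-12 estimate is biased under every implementation. The correction is still worth making, because the weighted analysis can displace the unweighted one as the basis for the primary interpretation.

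**What to change.** In SAP 3.1, and by reference in 3.2 and 3.3:

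1. Fit the probability that the record is observed separately at 3, 6 and 12 months, with the predictors already listed.
2. Apply each weight only to records of its own visit, and give month-0 records weight 1.
3. State that weights are applied at record level, not as a multiplier of each patient's whole likelihood.

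This keeps the change from month 0 as the target. The cost is two more logistic models and a few lines of SAP text, with no new data. One limit should be acknowledged: in a random-effects model, visit-specific weights remove the false month-0 difference and generally reduce the error in the change. They do not guarantee zero and are not better in every configuration.

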### **3. Primary Outcome Analyses**

#### **3.1. Analysis of intermediate factors**

Because the ISPU intervention was targeted to specific groups determined by baseline assessments, the primary analysis of the six intermediate factors will be restricted to the estimation of treatment differences among patients who were not in control at discharge, specifically assessing the percentage of patients with:

- 1) SBP below 130 mmHg at 3, 6, and 12-months among those with SBP of 130 mmHg or above at discharge
- 2) LDL below 70 mg/dL at 3, 6, and 12-months among those with LDL of 70 mg/dL or above at discharge

- 3) HbA1c below 7% at 3, 6, and 12 months among those with HbA1c of 7% or above at discharge
- 4) Smoking cessation at 3, 6, and 12-months among those smoking at dischargement,
- 5) Adhering to a Mediterranean or DASH diet among those not adhering at baseline
- 6) Having regular exercise levels of moderate or above among those with lower levels at baseline.

The primary hypothesis will focus on compliance/adherence at the 12-month visit, but mixed models will be used with assessments at the 3 time points (3, 6, and 12 months) and treatment differences reported at all three follow-up times.

Analyses will generally take the approach of using a mixed model approach with: 1) repeated measures at 3, 6 and 12 months, and 2) a random effect for patient and site (if models do not converge, site will be considered as affixed effect). As all of the intermediate factors will be dichotomized for the follow-up assessments, outcomes will be assessed using PROC GLIMMIX. Treatment differences will be assessed in a series of incremental models: 1) crude, 2) adjusted for stroke severity, 3) further adjustment for demographics, and 4) adjustment for cerebrovascular risk factors (see section 2 for factors in each group). The temporal pattern of treatment differences at 3, 6 and 12-months will be described by the treatment-specific proportion adherent/compliant with 95% confidence intervals. The primary assessment of treatment efficacy will be the p-value and confidence intervals for the treatment difference in the proportion at the 12th months; however, p-values and confidence intervals for months 3 and 6 will also be reported.

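### The SAP's weight standardisation omits the factor n: as written, the inverse-probability weights total 1, not the sample size that the same sentence claims.

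*SAP*

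**What the plan says.** SAP section 3.1 plans a weighted re-analysis of each of the six intermediate factors, both in patients not in control at discharge and in the whole population. The probabilities come from "a logistic regression model estimated in all subjects predicting the probability of observing the 12-month observation". The scaling step has two halves, an operation and the result claimed for it: the inverse of each probability is to be "standardized by dividing by the sum of the inverses, standardizing the inverse probabilities to have the same sum as the sample size". The sentence then concludes that statistical power is unaffected.

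The weights go into binary models: "As all of the intermediate factors will be dichotomized for the follow-up assessments, outcomes will be assessed using PROC GLIMMIX", with random effects for patient and site. Section 3.2 carries the weighting to dichotomised mRS, estimated "with both unadjusted and inverse-probability weighted adjustment". Section 3.3 carries it to SIS, which is continuous.

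Section 3.1 also provides that, where weighted and unweighted interpretations differ, the weighted one becomes primary and supplies the figures and estimates in the manuscript.

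**The concern.** The two halves of the scaling sentence describe different weights. In a binary likelihood with the dispersion fixed and model-based standard errors, the total weight acts as the amount of information, so the normalising constant sets the standard error. The SAP names neither a robust variance nor an estimated scale parameter, so the constant cannot be assumed harmless.

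The weighted results are more than a side analysis. They can become the primary interpretation, mRS is a primary outcome, and the SAP introduction treats the six factors as integral to the primary assessment. A mis-scaled standard error could itself create the difference in interpretation that triggers the switch.

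A second, quieter issue is that the probabilities are estimated in all subjects but used in several different analysis sets. The sentence does not say whose number the weights should sum to.

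**Working it through.** **1. The sum.** Let w_i = 1/p_i.
- Operation as written: sum_i [w_i / sum_j w_j] = 1 for any set of probabilities. The stated total, the sample size, is not reproduced.
- With the factor n: sum_i [n w_i / sum_j w_j] = n. This equals w_i / mean(w).

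This is algebra and needs no assumption. A simulation (n = 1,262, 21 sites, logistic missingness model, three assumed levels leaving 1,125, 956 or 773 observed) agreed: the literal weights summed to 1.000000 each time, and the corrected weights to exactly n.

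**2. Effect if coded literally, simple binary model.** Inputs: n = 1,262, the reduced sample in the protocol summaries, split 631 per arm (assumed equal); success rate 70% (assumed; the documents give no 12-month rates). SE of the log odds ratio = sqrt(2 / (n_arm x p x (1-p))).
- Weights summing to n: sqrt(2 / (631 x 0.21)) = 0.123.
- Weights summing to 1: sqrt(2 / (0.5 x 0.21)) = 4.36.
- Ratio: sqrt(1,262) = 35.5.

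The rate cancels from the ratio. At 50% the pair is sqrt(2 / (631 x 0.25)) = 0.113 and sqrt(2 / (0.5 x 0.25)) = 4.00.

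Fitting weighted logistic models to the simulated observed patients (50% v 60% success) gave the same pattern, with point estimates unchanged by the scaling:

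| Observed n | SE, sum = n | SE, sum = 1 | sqrt(n) |
|---|---|---|---|
| 1,125 | 0.1215 | 4.07 | 33.5 |
| 956 | 0.1309 | 4.05 | 30.9 |
| 773 | 0.1465 | 4.07 | 27.8 |

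**3. Allowing for site variance.** These are not the SAP's mixed models, and GLIMMIX was not run. A rough bound takes the variance as proportional to ICC + (1 - ICC)/m, with the site component unaffected by the weights. Inputs: ICC 0.05 (the protocol's planning value for SIS, borrowed here), 21 sites (SAP introduction), m = 1,262/21 = 60.1.
- Correct scaling: 0.05 + 0.95/60.1 = 0.0658.
- Literal scaling: 0.05 + 1,262 x 0.95/60.1 = 20.0.
- SE ratio: sqrt(20.0/0.0658) = about 17.

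That is about half the simple figure, and still unusable.

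**4. Where the constant does not matter.** In the 1,125 scenario, the cluster-robust SE was 0.1120 under either scaling. Weighted least squares for a continuous SIS-like outcome gave 0.4591 under either, because the residual variance is estimated.

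**5. Which n.** Three illustrations for 12-month data, under the assumed missingness and the simple model:
- Weights of the observed patients made to sum to 1,262: SEs are multiplied by sqrt(n_obs/1,262), that is 0.94, 0.87 and 0.78, so they are 6%, 13% and 22% too small.
- Weights scaled to sum to 1,262 over all subjects, then used in the observed: the raw sums were 1,262.7 of 1,428.0, 1,267.6 of 1,732.6 and 1,261.9 of 2,192.6. The observed totals are therefore 1,262 times these fractions: 1,116, 923 and 726. SEs are multiplied by sqrt(n_obs/total) = 1.004, 1.018 and 1.032, so they are up to about 3% too large.
- Weights scaled over the observed patients: the total equals n_obs and there is no distortion.

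Direction and size thus depend on the reading and on the missingness.

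**The case against.** The strongest reply is that the sentence corrects itself. It names the target and the purpose, so a statistician reading it whole would divide by the mean. If someone did code only the first half, standard errors some 17 to 35 times too large would stand out beside the unweighted fit, which the SAP also requires. This stands in large part. A reader might infer that the plan will run its weighted binary analyses as if there were one patient. The documents do not support that, since they state the opposite intention in the same sentence.

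It is also fair that the sqrt(n) factor comes from an independent-patient model with an assumed success rate, that modelling site variance reduces it, and that robust standard errors would remove it.

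A reader might further infer that SIS is affected because section 3.3 reuses the weighting. It is not, for the reason in step 4.

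Nor do the documents say that weights will be scaled to all subjects and then used in a subset. The probability model is fitted in all subjects, but the sample size in the scaling sentence can be read as that of the analysis being repeated. This is an ambiguity, not a stated error.

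What survives is the contradiction between operation and result, and the undefined n. The second is the less visible of the two, because errors of a few to some 20 per cent would look plausible.

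**Conclusion.** The rule is wrong as written. The operation in SAP section 3.1, carried to mRS in section 3.2, gives weights totalling 1, against the claimed total of the sample size; the factor n is missing. That conclusion rests on algebra alone.

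The consequence is conditional. It needs literal coding, a binary likelihood with fixed dispersion, and model-based standard errors. Under those conditions the standard errors would be inflated by up to about sqrt(n) in a simple model (35.5 at n = 1,262) and by roughly 17 under the borrowed ICC of 0.05. Point estimates in the simple model do not change.

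The unspecified n for the restricted subsets is a gap to close. Its size cannot be fixed from the documents, which give no 12-month completion rate.

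Because the weighted result can become the primary interpretation, the sentence should be corrected before the weighted models are programmed.

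**What to change.** Replace the scaling sentence with: w_i = n x (1/p_i) / sum_j(1/p_j), equivalently each inverse divided by the mean of the inverses. Take n and the sum over the patients whose weighted data enter that particular analysis, and recompute for each restricted and each whole-population analysis. Say explicitly whether patients without a 12-month observation, who can still contribute 3- and 6-month rows to the mixed model, belong to that set.

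The closing claim about power should also be softened. A total of n removes the artefact of scale, but unequal weights still cost some precision: in the three simulated scenarios the Kish effective sample sizes were 1,114.6 of 1,125, 903.6 of 956 and 728.2 of 773.

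The cost is one or two SAP sentences and one line of code. No data collection or design feature changes.
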